This study aimed to examine the extent to which working memory training improves aspects of cognition, the extent to which these effects are augmented by the participants' expectations or placebos, and whether any placebo effects are retained after participants become aware of their assigned expectations among a young adult population (ages 18-30). It was predicted that there would be a main effect of training, such that those who completed the true cognitive training intervention would improve in their cognition overall more than those who completed the control cognitive training, as well as a main effect of expectation, such that those who were given a positive expectation about their training would improve in their cognition overall more than those who received a negative expectation about their training. No interaction between training and expectations was predicted. It was also predicted that both the training and expectation effects would persist after being made aware of their expectations.

Secondary aims included exploring whether individual traits, including demographic characteristics, personality, or motivation, in young adults can predict the strength of placebo effects in cognitive training, and to determine the feasibility of this study with an older adult population (ages 60+). As these were exploratory analyses, no a priori predictions were made.

Study Design

The study design was a 2 (positive expectations vs. negative expectations) x 2 (true cognitive training intervention vs. control cognitive training intervention) between-subjects Randomized Controlled Trial (RCT). Thus, participants were assigned to one of four conditions: Positive expectations with true cognitive training, negative expectations with true cognitive training, positive expectations with control cognitive training, or negative expectations with control

cognitive training. For the older adult feasibility study, only the two true cognitive training conditions with either positive or negative expectations were used.

Recruitment Strategy

Participants for this study were recruited in two phases. The first phase included young adults (ages 18-30), who were recruited via university campus flyer advertisements and university human participant pools at each of the three study sites, University of Wisconsin – Madison, University of California, Irvine, and University of California, Riverside. The second phase included older adults (ages 60+), who were recruited through community flyer advertisements (e.g., senior community centers) and email advertisements to previous lab participants at each site.

Inclusion Criteria:

- Self-reported normal or corrected-to-normal vision
- No known neurological impairments (this includes any neurological impairments that would negatively impact participants' ability to perform perceptual or cognitive tasks or to complete long-term cognitive training; this could include neurological damage due to stroke in various brain areas; seizure conditions that would preclude the ability to view flashing images; motor control issues that preclude the ability to respond via button presses; etc.).
- Access to the internet, a computer, and a hand-held device, such as a cell phone or tablet

Exclusion Criteria:

- Self-reported non-normal or non-corrected-to-normal vision
- Neurological impairments
- No access to the internet, a computer, or a hand-held device

Procedure

Participants were first screened via email (young adults) or phone (older adults) to ensure they met all eligibility criteria. Young adults self-reported that they met eligibility criteria, while older adults were screened using the Montreal Cognitive Assessment Short – Abbreviated Telephone Version (MoCA), Geriatric Depression Scale – Short Form (GDS), and Geriatric Anxiety Scale – 10 Item Version (GAS).

During the first set of sessions, participants provided consent via an online form and then completed a pre-test cognitive battery (see Dependent Measures) online with a researcher present via Zoom. They also filled out a set of surveys about demographic information, personality traits, and other internal dispositions that may predict the extent to which they are susceptible to placebo effects.

After the pre-test, participants were assigned to their expectation group (positive/negative) and their training group (active/control), which was randomized prior to the start of the study. They were first given their group appropriate explicit expectation presented in a series of paragraphs and images online. Those in the positive expectation group were told that the training that would

complete has previous research supporting its use as a method to enhance cognitive abilities. Those in the negative expectation group were told that the training they would complete has previous research suggesting that it is unlikely to change cognitive abilities or may even decrease participants' scores on the tests of cognitive function. Note that depending on the participants' particular training group assignment, this may or may not have been deceptive. If they were assigned to the true cognitive training intervention, there is research showing that the to-be-utilized true training increases cognitive function. As such, those that received positive expectations received accurate information and those that receive negative expectations received inaccurate information. However, there is no research showing that the control training intervention increases cognitive function. As such, those that received negative expectations received accurate information and those that received positive expectations received inaccurate information.

The participants were then given instructions on how to complete their training task. Participants were asked to complete ten 20-minute sessions of training once per day without the presence of a researcher. The true cognitive training intervention was standard working memory (*n*-back) training task. In this task, participants were shown a series of colored circles one after another. As each circle appeared, their task was to indicate whether the color matched the one presented *n*-items back in the stream by tapping on the circle. For example, if they were performing a 3-back level, if they had seen the colors red, blue, green, and red, and then they saw the color blue, they would tap the screen. The control training intervention was a trivia/quiz task, which included general trivia questions.

After they completed 10 training sessions, they completed a "mid-test" session to complete a cognitive battery online with a researcher via Zoom. They were told that they would complete this cognitive battery as a "check-up" to see how their cognition had been changing during the study, and they were not told that it would be any different than the pre-test. However, in reality, for participants in the positive expectations groups, these tasks were altered to be easier than they were at pre-test to give the impression of cognitive improvement. For participants in the negative expectations groups, the tasks were made more difficult to give the impression of no change/degradation in cognition.

Participants were then asked to complete another set of 10 training sessions without the presence of a researcher before completing a post-test cognitive battery. All participants were then extensively debriefed; all deceptions were made clear, and participants were given an opportunity to ask any questions about the purpose of the study. About a week later, participants completed the cognitive battery one last time to examine whether any changes in cognitive function that were seen in the post-test persisted after the participants were informed about their expectations.

Study Timeline

Session(s)	Description	Approx. Day(s) of Study*
1	Cognitive battery pre-test Part 1	1
2	Cognitive battery pre-test Part 2 Individual difference questionnaires	2
3	Explicit expectation induction Training intervention instructions	3
4 -13	Cognitive training sessions Part 1 (20 min x 10 sessions; once per day)	4-13
14	Associative-learning cognitive battery “mid-test”	14
15 – 24	Cognitive training sessions Part 2 (20 min x 10 sessions; once per day)	15-24
25	Cognitive battery post-test Part 1	25
26	Cognitive battery post-test Part 2	26
27	Debriefing	27
28	Cognitive battery delayed-test Part 1	34
29	Cognitive battery delayed-test Part 2	35

*The length between study sessions varied across participants. 35 days was the minimum length to complete the study.

Dependent Measures

The main dependent measure consisted of a 12-task cognitive battery, 2 of which are control measures. Each of the tasks are described below.

1. The *n*-back task is a working memory measure in which participants view a series of letters and are asked to indicate whether the current letter is the same as the letter *n* items back. The *n*-back levels will vary between 1- and 3-back.
2. The O-Span task is a working memory measure in which participants alternate between completing simple math problems (e.g., 3+(2x2)) and viewing single letters. At the end of a given sequence, the participants are asked to recall all the letters that they had seen in the correct order. The number of letters to be recalled will range between 3 and 7.
3. The Task-Switching Task measures cognitive flexibility. On each trial, participants view a letter and a digit. The location of the pair instructs the participants to either categorize the letter as a consonant or vowel or else categorize the digit as even or odd.
4. The countermanding task is a cognitive flexibility task in which participants are presented with two types of stimuli on either the right or the left side of the screen and are required to tap on one of two buttons on either the same side as the stimulus or the opposite side of the stimulus.
5. The Useful Field of View (UFOV) is a measure of visual selective attention. Participants are briefly presented with a display consisting of a number of items on each of the four radial spokes and the four obliques; evenly spaced. One of the items is a target, while the remaining items are distractors. The participants' task is to indicate upon which of the 8 spokes the target appeared.

6. The Attentional Network Test (ANT) measures visual selective attention. On each trial, participants view a center arrow that faces either left or right. The arrow can be flanked on either side by either response compatible arrows (i.e., arrows facing in the same direction as the center arrow) or response incompatible arrows (i.e., facing the other direction). The participants' task is to indicate the direction that the center arrow is pointing.
7. The Mental Rotation Task measures spatial cognition. Participants are shown two images side by side. The images are either identical, but with one rotated relative to the other, or are mirror-reversed and rotated copies of one another. The participants' task is to indicate whether the two items are identical or are mirror-reversed copies.
8. The paper-folding task is a spatial cognition task in which the participant is shown a depiction of a piece of paper being folded various ways before a hole is punched in the paper. The participants' task is to indicate what the paper will look like when it is unfolded.
9. Raven's Advanced Progressive Matrices (RAPM) is a fluid intelligence measure in which the participant is presented with a grid of elements with one of the elements missing and is asked to identify the missing element that completes the grid pattern.
10. The UC Matrix Reasoning Task is a fluid intelligence measure, similar to RAPM, in which the participant is presented with a grid of elements with one of the elements missing and is asked to identify the missing element that completes the grid pattern.
11. The Mill-Hill Vocabulary scale is a control measure that assesses vocabulary ability.
12. The Shipley Institute of Living scale is also a control measure that assesses vocabulary ability.

Secondary measures used to determine whether individual characteristics predict placebo effects in cognitive training included demographic variables (e.g., age, gender, race/ethnicity), Big Five Inventory (BFI-10), Work and Family Orientation Scale (WOFO), Grit, Behavioral Avoidance/Inhibition scales (BIS/BAS), Theories of intelligence, Schutte Self-Report Emotional Intelligence Test, and Meta-Cognitive Skills Scale.

Statistical Analysis Plan

To examine the main hypotheses, a 2 (true cognitive training vs. control training) x 2 (positive expectation vs. negative expectation) MANCOVA will be conducted on the set of 10 dependent post-test variables, with pre-test scores as a covariate. Scores will be standardized prior to analysis. If significant, post hoc analyses will be conducted as necessary (i.e., it is unlikely that every DV will be similarly impacted by placebo effects - as such, follow-up analyses separated by DV will be performed after the main analysis). A similar analysis will be conducted on the delayed test scores (controlling for pre-test scores).

The following secondary variables will be analyzed to test for moderation of placebo effects on each DV: Big Five Inventory (BFI-10) subscale scores, Motivation (BIS/BAS) subscale scores, Grit scale score, Metacognitive scale score, Fixed/growth mindset scale score, Schutte Self-Report Emotional Intelligence Test subscale scores, Work and Family Orientation subscale scores, Demographic variables, such as age and gender.

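### After the debriefing, belief is likely to follow training arm, so the delayed-test training contrast estimates training plus disclosure, not training free of expectation

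*Combined protocol and SAP*

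**What the plan says.** Study Design crosses expectation with training: "The study design was a 2 (positive expectations vs. negative expectations) x 2 (true cognitive training intervention vs. control cognitive training intervention) between-subjects". Until the debriefing, assigned expectation is therefore balanced across training arms.

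Procedure makes the accuracy of the message depend on the arm. Depending on a participant's "particular training group assignment, this may or may not have been deceptive". For the true training, "there is research showing that the to-be-utilized true training increases cognitive function", so in those arms "those that receive negative expectations received inaccurate information". For the control training, "there is no research showing that the control training intervention increases cognitive function", so there the positive message was the inaccurate one.

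After the post-test, "All participants were then extensively debriefed; all deceptions were made clear". Study Timeline puts the debriefing at day 27 and the delayed battery at days 34 and 35.

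The opening statement of aims makes a prediction about that visit: "It was also predicted that both the training and expectation effects would persist after being made aware of their expectations". The Statistical Analysis Plan tests it as follows: "A similar analysis will be conducted on the delayed test scores (controlling for pre-test scores"). The documents describe no measure of belief after debriefing, no comparison group left undebriefed, and no qualification on how the delayed training term is to be read.

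**The concern.** The factorial design exists so that a training effect can be told apart from an expectation effect, and the trial predicts that expectation changes scores. A debriefing that corrects arm-dependent messages tends to give all true-training participants favourable information and all control participants unfavourable information. To that extent expectation is no longer balanced across training arms at the delayed test, although the analysis model is the same.

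What is at stake is how one term is interpreted. A delayed training effect could be reported as lasting benefit of training when part of it reflects what participants had just been told about their training.

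**Working it through.** The plan states no sample size, alpha, power or effect size, so it has no figure to reproduce. The check is cell algebra, followed by an illustration on assumed values.

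**Step 1: belief in each cell.** Code belief +1 (training supported) or −1 (not supported). Let u be the share of participants whose belief follows the disclosed facts; the rest keep their assigned expectation.

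| Cell | Before debriefing | Message accurate? | Disclosed | Mean belief after |
|---|---|---|---|---|
| True, positive | +1 | yes | +1 | +1 |
| True, negative | −1 | no | +1 | 2u − 1 |
| Control, positive | +1 | no | −1 | 1 − 2u |
| Control, negative | −1 | yes | −1 | −1 |

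Before debriefing, mean belief is 0 in both training arms, so its correlation with training is 0. Afterwards it is u in the true arms and −u in the control arms, and the correlation is u.

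**Step 2: the contrasts.** Let e be the positive-minus-negative expectation effect in SD, so one unit of belief is worth e/2.

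- Delayed training contrast = retained training effect + (u − (−u)) × e/2 = retained training effect + u × e.
- Delayed contrast by assigned expectation = ((1 − u) − (u − 1)) × e/2 = (1 − u) × e.

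**Step 3: size of u × e** (e and u are assumptions):

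| e (SD) | u = 0 | u = 0.25 | u = 0.5 | u = 1 |
|---|---|---|---|---|
| 0.1 | 0 | 0.025 | 0.05 | 0.10 |
| 0.2 | 0 | 0.05 | 0.10 | 0.20 |
| 0.3 | 0 | 0.075 | 0.15 | 0.30 |
| 0.5 | 0 | 0.125 | 0.25 | 0.50 |

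**Step 4: effect on the delayed test taken alone.** Assume no retained training effect, two-sided alpha 0.05, N = 200 in total, pre-test correlation 0.7 (residual variance 1 − 0.49 = 0.51), residual correlation 0.3 among the 10 tasks, and the same shift b on every task. The MANCOVA noncentrality is (N/4) × b²/0.51 × 10/(1 + 9 × 0.3), with 10 and 177 df.

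| b = u × e (SD) | Noncentrality | Chance of a significant training term |
|---|---|---|
| 0.05 | 0.66 | 6.9% |
| 0.10 | 2.65 | 14.3% |
| 0.20 | 10.60 | 54.6% |

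At b = 0.20 the chance is 25% for N = 100 and 90% for N = 400.

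**Step 5: what the planned analyses reveal about u × e.** Under this model the post-test expectation contrast is e and the delayed one is (1 − u) × e. Their difference is e − (1 − u) × e = u × e. If expectation effects also fade to a fraction r over the week, the added amount is r × u × e. The difference is then e − r(1 − u)e = (1 − r)e + r × u × e, too large by (1 − r)e. The difference would be too small if debriefing strengthened belief in the two accurately informed cells. With their belief at ±(1 + c), the added amount is u × e + c × e/2 and the difference is u × e − c × e/2. The difference indicates size; it is not a correction to subtract.

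**The case against.** Several points on the other side stand.

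- **The debriefing is intended.** The trial asks whether placebo effects survive awareness, and the delayed contrast by assigned expectation answers that. A reader might infer that the debriefing is an error and should be split, with the accuracy of the message withheld until after the delayed test. The documents do not support that: a split would weaken the awareness being tested and delay disclosure of a deception. Procedure is also written in the past tense, so the debriefings appear to have taken place.
- **Uptake may be small.** All 20 training sessions precede the debriefing, so an expectation effect that works through engagement in training cannot be created there. The induction combined a message with an altered mid-test, whereas the debriefing is one session. Controls learn only that supporting research is lacking, which is milder than the negative message they might have received.
- **The script is not in the documents.** A reader might infer that from day 27 every true-training participant holds a positive belief and every control participant a negative one, so that training and belief coincide. That is the limiting case u = 1. The content of the debriefing is itself inferred from the statement that all deceptions were disclosed, and what participants learn is whether research support exists, not whether the training works.
- **Step 4 does not give rates of false persistence claims.** Procedure asks whether changes seen at post-test persisted, so a training effect that appears only at the delayed test would not show persistence.
- **The other contrast carries information.** If the expectation effect persists in full, as predicted, then u is near 0 in this model and the training term is barely affected.

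Randomisation also still holds: the delayed contrast is a valid estimate of training plus truthful disclosure. But the persistence prediction for training concerns a different quantity, and the plan neither draws the distinction nor says how to check it.

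**Conclusion.** The point holds as a limit on interpretation. The delayed training contrast estimates the retained training effect plus u × e, not the expectation-free persistence of training that the aims predict. The size is unknown: 0 to 0.5 SD over the assumed ranges, with values near 0 credible. On the Step 4 assumptions, the chance of a significant delayed term with no retained training effect ranges from barely above nominal (6.9% at 0.05 SD) to more than half (54.6% at 0.20 SD).

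The conclusion rests on the debriefing having disclosed accuracy by arm, and on at least some participants updating their belief in a way that affects scores. The post-test training contrast is not touched, because it precedes debriefing. The delayed contrast by assigned expectation remains valid for whether the induced effect survives awareness. The older adult phase uses only true-training arms and so has no training contrast.

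**What to change.** Keep the debriefing as it is, and add to the Statistical Analysis Plan and the report:

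1. The delayed-test training term is defined as the effect of training plus truthful disclosure of its research support.
2. Claims about training free of expectation rest on the post-test training contrast.
3. Persistence of training is claimed only when the post-test training effect is also present.
4. The delayed training term is reported beside the post-test-to-delayed change in the expectation contrast, with confidence intervals, as an indication of the possible size of u × e. The text should say that this overstates u × e if expectation effects also fade naturally.

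The cost is a few sentences and one additional contrast from data already planned; no new data or procedure is needed. The downside is a more limited claim about delayed training benefit.

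### The training test includes the n-back paradigm that one arm practises, and no joint test covers the nine tasks that neither arm practises

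*Combined protocol and SAP*

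**What the plan says.** **Training.** The Procedure states: "The true cognitive training intervention was standard working memory (*n*-back) training task". In it, "participants were shown a series of colored circles one after another", and they respond to a match n items back. For the other arm, "The control training intervention was a trivia/quiz task". Ten sessions come before the mid-test. After it, "Participants were then asked to complete another set of 10 training sessions".

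**Outcomes.** Dependent Measures lists twelve tasks, two of them vocabulary control measures. Of item 1, the n-back, it says that the "task is a working memory measure in which participants view a series of letters". Item 2 is the only other task labelled as working memory: "The O-Span task is a working memory measure".

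**Analysis.** Under Statistical Analysis Plan, a two-by-two "MANCOVA will be conducted on the set of 10 dependent post-test variables", adjusted for pre-test scores. If it is significant, analyses by task follow as needed, because "it is unlikely that every DV will be similarly impacted by placebo effects". The delayed test is analysed in a similar way.

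**Prediction.** The opening aims predict a training main effect on overall cognition, an expectation main effect and no interaction. Both main effects are expected to persist after debriefing.

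**The concern.** The null hypothesis of the ten-variable training test is that all ten training effects are zero. An effect on one variable makes it false. Letter n-back shares its paradigm with the trained task and differs in its stimuli, so it is the outcome most open to a direct practice gain, and only one arm gets that practice.

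Rejection would then be statistically correct, but it would not show that training reached any other task. Including letter n-back is defensible as near transfer. What is missing is a test that separates near transfer from transfer to other tasks. At stake is how the training main effect and its persistence at the delayed test are read in the young-adult trial.

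**Working it through.** **Counts from the documents**
- Variables in the MANCOVA: 12 tasks − 2 control measures = 10, which reproduces the plan's figure. The plan does not name the ten, but items 1–10, including n-back, are the natural reading.
- Tasks that neither arm practises: 10 − 1 = 9.
- Training sessions: 10 + 10 = 20.

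**Assumptions (the documents give none of these)**
- Alpha 0.05; total N = 120, 200 or 300 in a balanced 2×2.
- All ten pre-test scores as covariates.
- Effects in residual SD units; equal residual correlation ρ between tasks, 0 or 0.3.

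**Formula.** For a 1-df contrast on p outcomes the test is an exact F with df1 = p and df2 = N − 4 − 10 − p + 1. Its noncentrality is λ = (N/4) · d′R⁻¹d. With one affected task, d′R⁻¹d = d² · [1 + (p − 2)ρ] / {(1 − ρ)[1 + (p − 1)ρ]}.

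**Worked case: N = 200, 0.5 SD on n-back only, p = 10**
- df2 = 200 − 4 − 10 − 10 + 1 = 177.
- ρ = 0: λ = 50 × 0.25 = 12.5; power 0.634.
- ρ = 0.3: λ = 12.5 × 3.4 / (0.7 × 3.7) = 16.4; power 0.780.
- Nine-task test: n-back is not among the outcomes, so λ = 0 and the rejection rate is alpha.

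Simulated rates for the ten-task test are slightly lower (0.612 and 0.753), because the formula ignores chance imbalance in the covariates.

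**Simulation, 3,000 trials per cell; entries are ρ = 0 / ρ = 0.3**

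| True training effect | Test | N = 120 | N = 200 | N = 300 |
|---|---|---|---|---|
| n-back 0.5 SD only | ten tasks | .343 / .448 | .612 / .753 | .845 / .940 |
| n-back 0.5 SD only | nine tasks | .056 / .048 | .047 / .044 | .054 / .053 |
| n-back 0.5 SD only | both significant | .054 / .048 | .047 / .044 | .053 / .053 |
| O-Span 0.5 SD only | nine tasks | .348 / .456 | .651 / .760 | .846 / .946 |
| n-back 0.5 + O-Span 0.3 SD | ten tasks | .459 / .561 | .765 / .860 | .947 / .980 |
| n-back 0.5 + O-Span 0.3 SD | nine tasks | .148 / .173 | .227 / .299 | .363 / .474 |

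Requiring the nine-task test as well keeps a false claim of transfer near 5%. The O-Span row shows the limit of that test: one affected task is enough to reject, so it shows transfer and not breadth.

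**Expectation and interaction.** With no true expectation or interaction effect, the ten-task expectation test rejected in .038–.054 of trials and the interaction test in .045–.060. Expectation is crossed with training, so n-back practice does not disturb them.

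**Planned follow-ups.** The plan states no multiplicity rule. Nine independent tests at an assumed unadjusted 0.05 give at least one false positive with probability 1 − 0.95⁹ = 0.37. With a true effect on n-back only, a significant ten-task test together with at least one falsely significant unpractised task occurs in about 20–35% of simulated trials.

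**The case against.** The follow-ups by task already go much of the way. The remark about placebo effects explains them but does not confine them to the expectation factor, so a reader would see n-back and each other task separately. A second MANCOVA is also not the only remedy. Bonferroni adjustment across the nine unpractised tasks holds false transfer at 4–6% under the same assumptions and names the affected task. With equal effects of 0.2 SD and ρ = 0.3, its power is 26%/44%/61% at the three sample sizes, against 18%/29%/44% for the nine-task MANCOVA. At ρ = 0 the order reverses: 35%/55%/76% against 57%/85%/98%. Finally, the nine-task test cannot establish an effect on overall cognition either.

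Most of this stands. The follow-ups would reveal n-back as a source, adjusted follow-ups would be a workable alternative, and breadth has to be handled by wording. It does not remove the point: the plan as written contains neither a joint test without n-back nor a multiplicity rule, so its follow-ups do not close the gap.

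**Conclusion.** The concern holds. That n-back is inside the joint test, and that no joint test leaves it out, follows from the documents. The only inference is that the ten variables are battery items 1–10. A significant training MANCOVA, at post-test or delayed test, would not by itself support the prediction about overall cognition or show transfer beyond the practised paradigm.

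The percentages rest wholly on assumed inputs. They show the mechanism and not how likely it is in this trial. The point is limited to the training main effect in the young-adult 2×2. It is an inexpensive improvement, not a flaw that invalidates the planned analysis.

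**What to change.** - Keep the planned ten-variable MANCOVA for training, expectation and interaction.
- For the training effect at post-test and at delayed test, pre-specify a MANCOVA on the nine tasks that neither arm practised, with the same covariates.
- Report letter n-back separately as the trained-paradigm (near-transfer) outcome.
- Claim transfer beyond the trained paradigm only if the nine-task test supports it.
- State that a result driven by any single task, n-back or other, does not support a claim about overall cognition.
- If outcome data have already been seen, date the addition and label it as such.

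The cost is one added analysis per time point on data already collected, plus SAP wording. The planned test and its power do not change. The claim becomes narrower if gains are confined to n-back. O-Span is the only task labelled as working memory in the added test, so power there is low if gains stay within working memory (last two rows of the table). If transfer is equal across tasks at 0.2–0.3 SD, the two tests differ in power by at most about 3 percentage points by the noncentral F formula; the largest gap is .590 against .560, at N = 120, 0.2 SD and ρ = 0.

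### Does the plan need a stated analysis for the two vocabulary control measures before an expectation effect can be interpreted?

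*Combined protocol and SAP*

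**What the plan says.** Dependent Measures describes a "12-task cognitive battery, 2 of which are control measures". The two controls are the last items on the list: "The Mill-Hill Vocabulary scale is a control measure that assesses vocabulary ability", and "The Shipley Institute of Living scale is also a control measure that assesses vocabulary ability". The documents say no more about what the two scales are meant to control for.

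Under Procedure, participants "completed a pre-test cognitive battery (see Dependent Measures"), take the battery again after the second block of training, and about a week after debriefing "participants completed the cognitive battery one last time". Vocabulary scores are therefore planned at all three time points.

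The Statistical Analysis Plan states that a 2 x 2 "MANCOVA will be conducted on the set of 10 dependent post-test variables", adjusted for pre-test scores and followed up by variable. It adds "A similar analysis will be conducted on the delayed test scores" and a list of personal characteristics that will be used to "test for moderation of placebo effects on each DV". Vocabulary and control measures are mentioned nowhere in that section.

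**The concern.** Expectation is one of the two manipulated factors, and participants are deliberately told what their training should do. If the positive-expectation groups scored higher on the ten ability tasks, a reader would ask whether they also scored higher on vocabulary, which a control measure suggests should not move. A shift there would point to something broader, such as effort or general engagement at testing, and would narrow what could be said about the ten abilities.

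The plan collects the scores needed to look at this but does not commit to looking. As written, the controls could be reported if null and left out if not. The same applies at the delayed test, where effects are predicted to persist after debriefing. Stating an analysis would cost a few sentences and a few extra models on data already scheduled, so the omission looks easy to criticise.

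**Working it through.** **Count of outcomes.** Inputs are the task list in Dependent Measures and the number of variables in the Statistical Analysis Plan.

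- Working memory 2, cognitive flexibility 2, visual selective attention 2, spatial cognition 2, fluid intelligence 2: total 10.
- Battery less controls: 12 − 2 = 10.

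Both counts reproduce the plan's figure of 10, so the MANCOVA set is the ten ability tasks and both vocabulary scales lie outside it. The plan does not list the ten variables, so this is an inference, but a secure one. Control scales with a stated main-effect analysis: 0 of 2.

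**What the omission touches.**

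| Planned element | Needs the vocabulary scales? |
|---|---|
| Training contrast, post-test, 10 tasks | No |
| Expectation contrast, post-test, 10 tasks | No |
| The same contrasts at delayed test | No |
| Follow-up by variable | No |
| Moderation by personal characteristics | No |
| A claim that the effect is confined to the ten abilities | Yes, but no hypothesis makes this claim |

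The opening section predicts improvement in cognition overall and predicts nothing for vocabulary. A vocabulary shift would not bias the contrast on the ten tasks. It would bear only on a later interpretation.

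**What a stated check could show.** The documents give no sample size and no correlations, so everything below rests on assumptions: N = 120, 200 or 300, equal groups, and residual correlation r between the two vocabulary scales of 0.3 to 0.7. For the expectation effect on the mean of the two scales, in residual SD:

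SE = (2/√N) × √((1 + r)/2), with t on N − 6 degrees of freedom.

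Example, N = 200 and r = 0.5: SE = 0.1414 × 0.866 = 0.1225; half-width of the 95% interval = 1.972 × 0.1225 = 0.242.

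| N | Half-width, r = 0.3 / 0.5 / 0.7 | Power at 0.2 residual SD, r = 0.3 / 0.5 / 0.7 |
|---|---|---|
| 120 | 0.292 / 0.313 / 0.333 | 27% / 24% / 22% |
| 200 | 0.225 / 0.242 / 0.257 | 42% / 37% / 33% |
| 300 | 0.183 / 0.197 / 0.210 | 57% / 51% / 46% |

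Power is from the noncentral t distribution, two-sided 5%. A null vocabulary result would therefore not exclude a modest general effect.

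A stricter check would compare the mean of the ten tasks with the vocabulary mean. Assume residual correlations of 0.3 among the ten, 0.5 between the vocabulary scales and 0.15 across the two sets, with one common residual SD. The variance of the difference is (1 + 9 × 0.3)/10 + (1 + 0.5)/2 − 2 × 0.15 = 0.37 + 0.75 − 0.30 = 0.82.

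SE = (2/√N) × √0.82 × √(1 + 12/(N − 17)), where the last factor allows for 12 pre-test covariates, with t on N − 16 degrees of freedom. Half-widths are 0.346, 0.261 and 0.210. Power for a true difference of 0.2 is about 21%, 33% and 46%. A modest effect that really was specific would usually not be told apart from zero.

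**The case for a change.** The strongest case for a change is that a measure called a control should come with a statement of what it controls for and how it will be read, fixed before results are seen. Follow-up is left open elsewhere in the section, so nothing else limits selective use of the two scales. The phrase about moderation on each outcome does not fill the gap: the plan's own outcome set is ten, and even a loose reading would give vocabulary only moderation tests. The cost is small, and the primary test and its alpha would not change.

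All of that is true as description. What does not follow is that the plan is defective. The role of testing specificity is itself a reading of one word; the scales could equally have been meant for the training contrast. For that contrast they are doubtful, because the control training is general trivia, which may bear on vocabulary.

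Nor would any pattern of results settle specificity. The negative message refers to tests of cognitive function in general, so a vocabulary shift could be a genuine expectation effect. Vocabulary may respond less to effort than the other tasks: if effort moved the ten tasks by 0.2 and vocabulary by half of that, the difference would be 0.2 − 0.1 = 0.1 with no specific effect at all.

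An equal-weight mean of the ten tasks is a debatable choice too, because the plan itself expects the tasks to be affected unequally. What stands is that the write-up would be clearer if the role of the two scales were stated.

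**Conclusion.** The concern does not call for a change. It is correct that 2 of the 12 tasks have no stated analysis at post-test or delayed test. If the plan is followed exactly, the randomised training and expectation contrasts on the ten ability tasks, and the conclusion about cognition overall, are sound. The missing piece is one that competent analysts would be expected to supply: the same 2 x 2 pre-test-adjusted model on the two vocabulary scales, reported beside the main analysis.

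This rests on two readings: that the ten variables are the ten ability tasks, and that no specificity claim is part of the hypotheses. It does not depend on the assumed sample sizes and correlations, which show only that the check would be informative about larger shifts and weak for modest ones. If a report did claim that an expectation effect was specific to the ten abilities, the vocabulary estimates and their intervals would belong next to that claim.
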